## 7. Contraception provisions:

**Females:** Due to the teratogenic potential of LEN, FCBP must follow the rules listed below (otherwise excluded):

### **Applicable in all countries except the US:**

- a. Not be pregnant as confirmed by a negative serum pregnancy test at screening and a medically supervised urine pregnancy test prior to starting study therapy
- b. Refrain from breast feeding and donating oocytes during the study and for 3 months after the last dose of study drug or according to local guidelines for LEN, whichever is longer
- c. Agree to ongoing pregnancy testing during the course of the study, and after study treatment has ended. This includes pregnancy testing and counseling if a patient misses her period or if there is any abnormality in her menstrual bleeding and applies even if the patient practices complete sexual abstinence
- d. Commit to continued abstinence from heterosexual intercourse if it is in accordance with her lifestyle (which must be reviewed on a monthly basis) or agree to use and be able to comply with the use of highly effective contraception without interruption at least 4 weeks prior to start of study drugs, during the study treatment and for 3 months after the last dose of study drug, or, for LEN, according to the local guidelines, whichever is longer

### **Applicable in the US:**

- e. Not be pregnant as confirmed by pregnancy tests performed before treatment initiation, within 10-14 days and again within 24 hours of initiating treatment (even if true abstinence is the chosen method of birth control)
- f. Refrain from breast feeding and donating oocytes during the study and for 3 months after the last dose of study drug, or according to US guidelines for LEN, whichever is longer
- g. Agree to ongoing pregnancy testing during the study (every 4 weeks in women with regular menstrual cycle and every two weeks in women with irregular menstrual cycle), and after study therapy has ended (even if true abstinence is the chosen method of birth control). This includes pregnancy testing and counseling if a patient misses her period or if there is any abnormality in her menstrual bleeding.
- h. Not get pregnant while taking the study treatment and for at least 3 months after the last dose of study treatments by using at the same time 2 effective methods of contraception, at least one highly effective method and one additional effective method (see [Appendix 13: Contraceptive Guidance and Collection of Pregnancy Information](#)), each time engaging in sexual activity with a male, starting at least 4 weeks before taking the study treatment, while taking the study treatment, during breaks (dose interruptions) and for at least 3 months after stopping the study treatment, or for LEN, according to the US guidelines, whichever is longer. True abstinence from heterosexual sexual intercourse is also an acceptable method of contraception. The use of emergency contraception is also permitted

8. Due to the teratogenic potential of lenalidomide, male participants must follow the rules listed below (otherwise excluded):

**Applicable in all countries except the US:**

- a. Use an effective barrier method of contraception without interruption if the patient is sexually active with a FCBP. Male patients should refrain from donating sperm during the study participation and for 3 months after the last dose of study treatment, or according to the local guidelines for LEN, whichever is longer

**Applicable in the US:**

- b. Use a latex or synthetic condom each time they have sex with a FCBP. True abstinence from heterosexual sexual intercourse is also an acceptable method of contraception. The use of emergency contraception is also permitted. Male patients should refrain from donating sperm during the study participation and for 3 months after the last dose of study drug, or according to the US guidelines for LEN, whichever is longer

### Statistical Analysis

A Primary analysis will be performed when all enrolled patients have either completed C3D28 or discontinued the study prior to C3D28 for any reason. Final analysis will be performed at the end of the study.

Any deviations from the statistical analysis outlined in this protocol will be described, and reasons for the deviations listed, in the clinical study report.

Details of the analyses to be performed on data from this study will be provided in a separate SAP.

### End of Study

The end of the study is reached when all patients still on study treatment have been followed for at least 3 years, or when the final patient on study has completed their last visit, whichever comes first.

Patients who are receiving ongoing treatment at the end of study may continue treatment with either of the options below upon assessment of a clinical benefit of continued treatment by the investigator and in accordance with the local regulatory guidance:

- commercially available tafasitamab for the approved dose regimen locally; or
- participation in the tafasitamab extension study if above option is not available.

Upon study closure, Incyte will notify the applicable regulatory agencies in accordance with local requirements.

End of study visit for a patient: An end of study visit for a patient is defined as the visit taking place when the patient has completed 90-day safety follow up after the last tafasitamab dose given.

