## 2 SCHEDULE OF ASSESSMENTS (SoA)

**Table 3: Schedule of Assessments**

Evaluation or Procedure	Screening Period	Treatment Period (Cycle = 28 days)												Follow-Up Period
	Screening ≤28 Days prior to D1	Cycle 1			Cycle 2		Cycle 3		Cycle 4-12	Cycle 12	Cycle 13 onwards	End of Treatment Visit (EOT) 	90-Day Safety Follow-up Visit/ End of Study Visit 	
Day	Screen	D1	D4 ±1 day	D8 ±1 day	D15 ±1 day	D1 ±1 day	D15 ±1 day	D1 ±1 day	D15 ±1 day	D1 ±2 days	D28 ±2 days	D1 ±2 days	Within 14 days after decision on treatment discontinuation	±7 days
Starting Evaluations and Eligibility														
Informed consent	X													
Inclusion/exclusion criteria	X	X 												
Demography	X													
Medical history/current medical condition	X													
Disease history/staging/Ann Arbor	X													
Disease risk assessment (IPI)	X													
Throughout Evaluations														
Prior/concomitant therapy 	X	X	X	X	X	X	X	X	X	X		X	X	X
Physical examination (F – full, L – limited)	F	L						L		L 		L 	F	
ECOG performance status	X	X 				X		X		X			X	
Body weight/height 		X	X	X	X	X	X	X	X	X		X	X	
B-symptoms	X	X				X		X		X		X	X	
Vital signs 	X	X	X	X	X	X	X	X	X	X		X	X	
12-lead resting ECG	X	X 			X 	X 		X 		X 5a			X	
Adverse events (AEs, SAEs and AESIs)	X	X	X	X	X	X	X	X	X	X		X	X	X
Laboratory														
Urinalysis (local lab)	X	X				X		X		X			X	
Pregnancy test (FCBP) 	X	X 		X 	X 	X 		X 		X 		X 	X	
Pregnancy and risks counselling	X	X				X		X		X			X	
US only: pregnancy and risk interview	X	X				X		X		X			X	
Hematology and Serum chemistry (local lab) 	X	X	X	X	X	X	X	X	X	X		X	X	
Serology Hepatitis B (local lab)	X													

Evaluation or Procedure	Screening Period	Treatment Period (Cycle = 28 days)												Follow-Up Period
	Screening ≤28 Days prior to D1	Cycle 1				Cycle 2		Cycle 3		Cycle 4-12	Cycle 12	Cycle 13 onwards	End of Treatment Visit (EOT) 	90-Day Safety Follow-up Visit/ End of Study Visit 
Day	Screen	D1	D4 ±1 day	D8 ±1 day	D15 ±1 day	D1 ±1 day	D15 ±1 day	D1 ±1 day	D15 ±1 day	D1 ±2 days	D28 ±2 days	D1 ±2 days	Within 14 days after decision on treatment discontinuation	±7 days

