From Cycle 4 onwards, blood samples for tafasitamab anti-drug antibodies (ADAs) will be collected pre-dose on D1 of every other cycle until Cycle 12, i.e. Cycle 4, Cycle 6, Cycle 8, Cycle 10, Cycle 12.

Tafasitamab PK sample will be taken pre-dose and 30 min  $\pm$  15 min after the end of tafasitamab infusion.

10aTafasitamab PK samples will be taken pre-dose and 30 min  $\pm$  15 min after the end of tafasitamab infusion on C4D1 and afterwards pre-dose on D1 of every other cycle until Cycle 12, i.e. Cycle 6, Cycle 8, Cycle 10, Cycle 12.

PET-CT or PET-MRI should be performed at screening, at C12D28 ( $\pm$  4 days) and at EOT visit unless disease progression was already radiologically confirmed prior to the EOT visit. If progression/relapse is suspected on the basis of clinical symptoms, PET-CT or PET-MRI should be performed to confirm disease progression. PET/CT or PET-MRI from Cycle 25 onwards should be performed only if deemed necessary, and not more than once per year.

11aCT or MRI should be performed within 4 days prior to C3D1, C5D1, C7D1 and C10D1. From Cycle 13-24 CT or MRI should be performed approximately every 3 months  $\pm$  2 days from the previous scan. The first assessment during this phase will take place 3 months  $\pm$  2 days after C12D28. From Cycle 25 onwards: approximately once every year  $\pm$  2 weeks from the previous scan.

Repeat bone marrow biopsy only in those patients who had known bone marrow involvement at screening to confirm a CR. If repeat bone marrow biopsy is required to confirm CR, the assessment should be done at C3D15  $\pm$  1 day and/or within 15 days after C5D1, C7D1, C10D1 and C12D28. Bone marrow assessment from Cycle 13 to 24 approximately every 3 months  $\pm$  2 weeks from the previous assessment to be performed to confirm a CR only in those patients who had known marrow involvement at screening.

Tafasitamab infusions should be given after pre-medication administration 30–120 minutes prior to starting the infusion. For patients who do not experience any grade 2 or higher IRRs with their first four infusions, pre-medication at subsequent treatments may be omitted according to institutional treatment guidelines.

Regardless of the reason for study treatment discontinuation, patients will have a safety follow-up visit or phone call scheduled 90 days after the last dose of the study treatment.

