## 9 STUDY ASSESSMENTS AND PROCEDURES

Study procedures and their timing are summarized in [Section 2](#).

Adherence to the study design requirements, including those specified in the SoA (see [Section 2](#)), is essential and required for study conduct.

Protocol waivers or exemptions are not allowed, except where necessary to eliminate an immediate hazard to study patients.

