##### ***9.4.7.1 Time Period and Frequency for Collecting AE, SAE and AESIs Information***

All AEs, SAEs and AESIs will be collected and recorded in eCRF from the signing of the ICF until the end of study visit.

If the investigator learns of any SAE/AESI, including a death, at any time after a patient has completed the study, and he/she considers the event to be reasonably related to the study treatment or study participation, the investigator must promptly notify the sponsor.

Medical occurrences that begin before obtaining informed consent will be recorded on the Medical History/Current Medical Conditions section of the eCRF not the AE section.

All SAEs and AESIs will be reported to the sponsor or designee within 24 hours, as indicated in [Appendix 12: AEs: Definitions and Procedures for Recording, Evaluating, Follow-Up, and Reporting](#). The investigator will submit any updated SAE and AESI data to the sponsor within 24 hours of it being available.

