### 12.3 Appendix 3: Study Specific Definitions

For the purposes of this protocol, **primary refractory disease** is defined as a disease progressing in the course of the first line treatment as per International Working Group response criteria (Cheson *et al.*, 2007), and/or, showing a response of less than a PR to first-line treatment or disease recurrence/progression within  $\leq 6$  months from the completion of first-line therapy.

**Disease refractory to last treatment** is defined as having had less than a PR to the most recently administered systemic therapy.

**Relapsed/progressive/recurrent disease** reflects the appearance of any new lesions or increase by  $\geq 50\%$  of previously involved sites from nadir according to the International Working Group response criteria (Cheson *et al.*, 2007), after the most recent systemic therapy.

**First act of recruitment (EU):** For purposes of EU clinical trial regulation (536/2014) the first act of recruitment of a potential patient is defined as the date of initiation of the first site.

**Start of study:** A patient is considered to have started the study and entered the screening period when they have signed the informed consent form.

**End of Treatment:** The end of treatment is defined as the date when the patient has received last tafasitamab dose. An end of treatment visit will be performed within 14 days after decision on treatment discontinuation.

**End of Study:** The end of the study is reached when all patients still on study treatment have been followed for at least 3 years, or when the final patient on study has completed their last visit, whichever comes first.

Patients who are receiving ongoing treatment at the end of study may continue treatment with either of the options below upon assessment of a clinical benefit of continued treatment by the investigator and in accordance with the local regulatory guidance:

- commercially available tafasitamab for the approved dose regimen locally; or
- participation in the tafasitamab extension study if above option is not available

**End of study visit for a patient:** An end of study visit for a patient is defined as when the patient has completed 90 day safety follow up after the last tafasitamab dose given.

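### The visit that closes adverse-event collection has two start points, and one of them can cut off the end of the primary-endpoint TEAE window when lenalidomide stops after tafasitamab

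*Protocol*

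**What the plan says.** **When AE collection ends.** Protocol 9.4.7.1: "All AEs, SAEs and AESIs will be collected and recorded in eCRF from the signing of the ICF until the end of study visit". After that, the investigator need only notify SAEs and AESIs that come to light and are considered related ("If the investigator learns of any SAE/AESI, including a death, at any time after a patient has completed the study" opens that rule).

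**When that visit takes place, definition A (tafasitamab).** The Protocol Synopsis (End of Study) and Section 7.12 define the patient's end-of-study visit as "the visit taking place when the patient has completed 90-day safety follow up after the last tafasitamab dose given". Appendix 3 repeats it: "when the patient has completed 90 day safety follow up after the last tafasitamab dose given". Appendix 3 also ties end of treatment to the same drug: "The end of treatment is defined as the date when the patient has received last tafasitamab dose".

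**When that visit takes place, definition B (study treatment).** The SoA has one column for this visit, "90-Day Safety Follow-up Visit/ End of Study Visit". Its footnote 14 says "patients will have a safety follow-up visit or phone call scheduled 90 days after the last dose of the study treatment". Protocol 5.1 and SAP Section 3 make the same visit mandatory on the same count.

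**The primary endpoint.** The primary estimand, Protocol 10.3.7.1 and SAP 10.2.1.3 all run the TEAE window to 90 days past the final dose of study treatment. SAP 4.2.5 defines that dose as the last nonzero dose of either component. Its worked example has LEN ending after tafasitamab.

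**The concern.** One visit has two dates, and it closes collection for the primary endpoint. The two dates differ whenever the last LEN dose falls after the last tafasitamab dose. The documents show two routes to this:

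- Both drugs stop in the same cycle. Protocol 7.3.2 lets LEN run to Day 21, whereas the last tafasitamab visit in a cycle is earlier.
- Tafasitamab stops and LEN continues alone, as Protocol 7.3.1.3 and 7.3.1.4 allow after severe infusion reactions or cytokine release syndrome.

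A site using definition A could then end collection while the TEAE window is still open. The events exposed are mainly non-serious ones, and SAEs or AESIs not judged related, that first appear or worsen late in the tail. The analysis cannot recover events that were never collected.

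**Working it through.** The plan gives no figure on this point, so the check is date arithmetic.

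**Notation.** T is the day of the last tafasitamab dose and L the day of the last LEN dose. Study day of Cycle x Day y = 28(x − 1) + y.

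- TEAE window ends at L + 90 when L is later than T (SAP 10.2.1.3 with 4.2.5).
- Visit under definition A: T + 90.
- Visit under definition B: L + 90, a nominal gap of 0 days.

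**Cap on the loss.** The SoA schedules AE recording at the treatment visits where LEN is dispensed. Protocol 7.3.3.1 evaluates AEs at each visit, and Protocol 5.1 places the end-of-study visit after treatment discontinuation. If collection therefore stays open at least to day L:

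missed tail ≤ (L + 90) − max(T + 90, L) = min(90, L − T).

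**Assumptions for the examples.** Dosing falls on SoA visit days, LEN is taken to Day 21, and there are no delays. The tafasitamab dosing table is redacted. Day 1 only from Cycle 4, and Day 15 as the last infusion day in Cycles 1–3, are read from the SoA visit columns.

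| Case | T | L | T + 90 | L + 90 | Missed tail |
|---|---|---|---|---|---|
| Same cycle, Day 15 then Day 21 (Cycle 2) | 43 | 49 | 133 | 139 | 6 days |
| SAP 4.2.5 example | 13 Apr 2022 | 20 Apr 2022 | 12 Jul 2022 | 19 Jul 2022 | 7 days |
| Same cycle, Day 1 then Day 21 (Cycle 4) | 85 | 105 | 175 | 195 | 20 days (20/90 = 22%) |
| LEN alone one more cycle (C8D1, C9D21) | 197 | 245 | 287 | 335 | at most 48 days |
| LEN alone two more cycles (C8D1, C10D21) | 197 | 273 | 287 | 363 | at most 76 days |
| LEN alone three more cycles (C8D1, C11D21) | 197 | 301 | 287 | 391 | L − T = 104, capped at 90 |

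**Visit window.** The SoA allows ±7 days. For the 20-day case, the two actual visit dates can lie between 20 − 14 = 6 and 20 + 14 = 34 days apart.

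**Without the cap.** Read literally, definition A can place the visit while LEN is still being taken. With the last tafasitamab on C1D15 (day 15) and LEN to C12D21 (day 329), the visit is day 105 and the window ends on day 419. The gap is 314 days, of which 329 − 105 = 224 are days on LEN. This is an outer bound, not an expectation.

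**Patients with no loss.** If tafasitamab ends on or after the last LEN dose, as in monotherapy after Cycle 12, the two definitions coincide.

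**The case against.** The best counter-argument is that every operative instruction uses definition B. The primary estimand itself directs collection to 90 days past the final dose of study treatment. Protocol 5.1 makes that visit mandatory, and footnote 14 sits on the column that carries the end-of-study name. Protocol 10.3.7.1 equates the end of the TEAE window with the end of the study. Protocol Section 9 requires "Adherence to the study design requirements, including those specified in the SoA". On this view, definition A is one sentence copied three times, written for the usual course in which tafasitamab outlasts LEN.

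Much of this stands. A site following the SoA has no nominal gap, so data loss is possible, not certain. Further points also stand:

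- The ±7-day window remains under either definition. A visit 7 days early leaves up to 7 days uncovered, so the 6- and 7-day examples are no larger than what the fix leaves.
- The 20-day case is a ceiling for stopping both drugs in one cycle, because LEN may stop before Day 21.
- The cap assumes a site that keeps collecting during LEN under the SoA yet dates the visit by the other definition.
- Protocol 7.3.1 discontinues study drugs after two consecutive skipped tafasitamab doses in the first three cycles, which may limit how often LEN continues alone.

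The argument does not remove the contradiction. Section 9.4.7.1 closes collection at the end-of-study visit. The passages that formally define that visit, including the definitions appendix, use tafasitamab. Nothing ranks the SoA above them, so a careful site can reach either date.

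**Conclusion.** The concern holds. The end of collection for the primary endpoint depends on which protocol passage a site applies. The effect is conditional and bounded: 0 days nominally under the SoA, and at most min(90, L − T) days of the tail under the tafasitamab definition if collection stays open during LEN. On the stated dosing assumptions, that is 6 or 20 days when both drugs stop in one cycle, and up to 48 or 76 days after one or two further cycles of LEN alone.

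These are days at risk, not events. No percentage-point effect can be given: SAP 10.2.4.1.1 runs the primary safety analysis on the Primary Analysis Set, and neither its size nor the number of affected patients is stated. Related SAEs and AESIs learned of later must still be notified, and a repeated TEAE counts once at its worst, which limits the loss further. The direction is under-counting. The plan should be corrected, but this does not undermine the trial.

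**What to change.** Reconcile the end-of-study visit definition in the Protocol Synopsis, Section 7.12 and Appendix 3 with footnote 14, Protocol 5.1, the primary estimand and SAP Section 3. The visit that closes AE collection should fall 90 days after the last dose of any study drug, the start point the TEAE definition already uses.

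For consistent labels only, SAP 10.2.1.4 should count from the last date of study treatment in SAP 4.2.5. It now counts from end of treatment, which SAP 4.2.3 and Appendix 3 tie to tafasitamab. The end-of-treatment definition can stay for its other uses.

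The cost is wording in three protocol passages and one SAP line. Sites that used the tafasitamab definition would make a later safety contact, later by L − T days, for patients whose LEN ended last. Sites already following footnote 14 change nothing. The nominal gap becomes 0 days, and only the ±7-day visit tolerance remains. No treatment rule changes. How Protocol 7.3.1 fits with 7.3.1.3 and 7.3.1.4 on continuing LEN alone is a separate matter, and those passages must be reconciled in their own right.

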## 2 SCHEDULE OF ASSESSMENTS (SoA)

**Table 3: Schedule of Assessments**

Evaluation or Procedure	Screening Period	Treatment Period (Cycle = 28 days)												Follow-Up Period
	Screening ≤28 Days prior to D1	Cycle 1			Cycle 2		Cycle 3		Cycle 4-12	Cycle 12	Cycle 13 onwards	End of Treatment Visit (EOT) 	90-Day Safety Follow-up Visit/ End of Study Visit 	
Day	Screen	D1	D4 ±1 day	D8 ±1 day	D15 ±1 day	D1 ±1 day	D15 ±1 day	D1 ±1 day	D15 ±1 day	D1 ±2 days	D28 ±2 days	D1 ±2 days	Within 14 days after decision on treatment discontinuation	±7 days
Starting Evaluations and Eligibility														
Informed consent	X													
Inclusion/exclusion criteria	X	X 												
Demography	X													
Medical history/current medical condition	X													
Disease history/staging/Ann Arbor	X													
Disease risk assessment (IPI)	X													
Throughout Evaluations														
Prior/concomitant therapy 	X	X	X	X	X	X	X	X	X	X		X	X	X
Physical examination (F – full, L – limited)	F	L						L		L 		L 	F	
ECOG performance status	X	X 				X		X		X			X	
Body weight/height 		X	X	X	X	X	X	X	X	X		X	X	
B-symptoms	X	X				X		X		X		X	X	
Vital signs 	X	X	X	X	X	X	X	X	X	X		X	X	
12-lead resting ECG	X	X 			X 	X 		X 		X 5a			X	
Adverse events (AEs, SAEs and AESIs)	X	X	X	X	X	X	X	X	X	X		X	X	X
Laboratory														
Urinalysis (local lab)	X	X				X		X		X			X	
Pregnancy test (FCBP) 	X	X 		X 	X 	X 		X 		X 		X 	X	
Pregnancy and risks counselling	X	X				X		X		X			X	
US only: pregnancy and risk interview	X	X				X		X		X			X	
Hematology and Serum chemistry (local lab) 	X	X	X	X	X	X	X	X	X	X		X	X	
Serology Hepatitis B (local lab)	X													

Evaluation or Procedure	Screening Period	Treatment Period (Cycle = 28 days)												Follow-Up Period
	Screening ≤28 Days prior to D1	Cycle 1				Cycle 2		Cycle 3		Cycle 4-12	Cycle 12	Cycle 13 onwards	End of Treatment Visit (EOT) 	90-Day Safety Follow-up Visit/ End of Study Visit 
Day	Screen	D1	D4 ±1 day	D8 ±1 day	D15 ±1 day	D1 ±1 day	D15 ±1 day	D1 ±1 day	D15 ±1 day	D1 ±2 days	D28 ±2 days	D1 ±2 days	Within 14 days after decision on treatment discontinuation	±7 days
Serology Hepatitis B, DNA, if indicated (local lab)	X 					X 		X 		X 			X 	
Serology Hepatitis C (local lab)	X													
Coagulation (aPTT or PTT, PT and/or INR) (local)	X									C4D1			X	
Thyroid Stimulating Hormone (TSH-local lab) 	X									C4D1			X	
Tafasitamab ADAs		X 				X 		X 		X  ,	X 		X 	
PK tafasitamab		X 	X 	X 	X 	X 	X 	X 	X 	X 10a ,	X 		X 	
CD19 expression 	X													
Imaging and Tumor Evaluation														
PET-CT or PET-MRI	X										X 	X 	X 	
CT or MRI								X 11a		X 11a		X 11a		
Biopsy/Tissue														
Tissue sample collection for central pathology review	X													
Bone marrow aspiration & biopsy	X 								X 	X 	X 	X 		
Drug Administration														
LEN capsules allocation (Incl. patient home intake record)		X				X		X		X				

Abbreviations: AE=adverse event; ADA=Anti-drug antibodies; AESIs=adverse events of special interest; aPTT= activated partial thromboplastin time; anti-HBc=hepatitis B core antibody; β-HCG=beta-human chorionic gonadotropin; C=cycle; CT=computed tomography; D=day; ECG=electrocardiogram; ECOG=Eastern Cooperative Oncology Group; eCRF=electronic case report form; EOS=end of study; EOT=end of treatment; F=full physical examination; FCBP=female of childbearing potential; HBV=hepatitis B virus; INR=international normalized ratio; IP=International Prognostic Index; IRRs=infusion-related reactions; L=limited physical examination; LEN=lenalidomide; MRI=magnetic resonance imaging; PE=physical examination; PET=positron emission tomography; PK=pharmacokinetics; PT=prothrombin time; PTT=partial thromboplastin time; SAE=serious adverse event TSH=Thyroid stimulating hormone

Before study treatment administration.

Previous/Concomitant therapy will be recorded as per [Section 7.8](#). After disease progression only anticancer treatments and other relevant concomitant medications, i.e., used for treatment of an AE (at the discretion of the investigator) should be entered.

A limited PE (L) will be performed on Day 1 of every other Cycle, e.g., Cycle 5, Cycle 7, Cycle 9, Cycle 11. From Cycle 13 onwards, a limited PE will only be performed at the discretion of the investigator if directed by any clinical symptoms or adverse events.

Body height will be measured at Cycle 1 Day 1 only. Body weight can be measured up to 24 hours prior to the study treatment administration.

12-lead resting ECG performed within 3 hours after the end of tafasitamab infusion.

5aA 12-lead resting ECG will be performed (within 3 hours after the end of tafasitamab infusion.) on D1 of every third cycle until Cycle 12, i.e., Cycle 6, Cycle 9 and Cycle 12.

Pregnancy tests: A serum ( $\beta$ -HCG)/urine pregnancy test is mandatory only for females of childbearing potential (FCBP). A serum pregnancy test will be performed locally at Screening and at the End of treatment visit. At all other indicated time points, a urine pregnancy test for FCBP will be performed locally and the result must be negative for dosing. At Cycle 1 Day 1 pregnancy test must be performed within 24 hours prior to the start of study treatment. For US only, a pregnancy test at screening must be performed within 10 to 14 days prior to the start of study treatment. For US FCBP with irregular menstrual cycle a urine pregnancy test will be performed every two weeks. A home urine pregnancy test kit and the home urine pregnancy test diary will be handed out to the US FCBP with irregular menstrual cycle on Cycle 2 Day1 to Cycle 12 Day1. Pregnancy testing and counseling must be performed if a patient misses her period or if there is any abnormality in her menstrual bleeding. Lenalidomide treatment must be discontinued during this evaluation. Patients reaching end of treatment during Cycle 1 – Cycle 12 a serum pregnancy test will be performed at-least 4 weeks after the last dose of study drug, in accordance with the Lenalidomide SmPC/USPI.

Sample to be collected and evaluated in the local laboratory (can be done on the day before study treatment administration) and reviewed by study treating physician before study treatment administration.

HBV-DNA to be measured at screening and re-measured at subsequent visits only if anti-HBc was positive at screening.

From Cycle 4 onwards, blood samples for tafasitamab anti-drug antibodies (ADAs) will be collected pre-dose on D1 of every other cycle until Cycle 12, i.e. Cycle 4, Cycle 6, Cycle 8, Cycle 10, Cycle 12.

Tafasitamab PK sample will be taken pre-dose and 30 min  $\pm$  15 min after the end of tafasitamab infusion.

10aTafasitamab PK samples will be taken pre-dose and 30 min  $\pm$  15 min after the end of tafasitamab infusion on C4D1 and afterwards pre-dose on D1 of every other cycle until Cycle 12, i.e. Cycle 6, Cycle 8, Cycle 10, Cycle 12.

PET-CT or PET-MRI should be performed at screening, at C12D28 ( $\pm$  4 days) and at EOT visit unless disease progression was already radiologically confirmed prior to the EOT visit. If progression/relapse is suspected on the basis of clinical symptoms, PET-CT or PET-MRI should be performed to confirm disease progression. PET/CT or PET-MRI from Cycle 25 onwards should be performed only if deemed necessary, and not more than once per year.

11aCT or MRI should be performed within 4 days prior to C3D1, C5D1, C7D1 and C10D1. From Cycle 13-24 CT or MRI should be performed approximately every 3 months  $\pm$  2 days from the previous scan. The first assessment during this phase will take place 3 months  $\pm$  2 days after C12D28. From Cycle 25 onwards: approximately once every year  $\pm$  2 weeks from the previous scan.

Repeat bone marrow biopsy only in those patients who had known bone marrow involvement at screening to confirm a CR. If repeat bone marrow biopsy is required to confirm CR, the assessment should be done at C3D15  $\pm$  1 day and/or within 15 days after C5D1, C7D1, C10D1 and C12D28. Bone marrow assessment from Cycle 13 to 24 approximately every 3 months  $\pm$  2 weeks from the previous assessment to be performed to confirm a CR only in those patients who had known marrow involvement at screening.

Tafasitamab infusions should be given after pre-medication administration 30–120 minutes prior to starting the infusion. For patients who do not experience any grade 2 or higher IRRs with their first four infusions, pre-medication at subsequent treatments may be omitted according to institutional treatment guidelines.

Regardless of the reason for study treatment discontinuation, patients will have a safety follow-up visit or phone call scheduled 90 days after the last dose of the study treatment.

EOT samples for PK and ADA will not be collected for patients receiving tafasitamab treatment beyond Cycle 12.

Vital signs include temperature, systolic and diastolic blood pressure, pulse and respiratory rate. Vital signs are to be obtained immediately pre-tafasitamab infusion, and during infusion (15  $\pm$  5, 30  $\pm$  10, and then every 60  $\pm$ 15 minutes), at the end of infusion ( $\pm$  20 minutes) and as clinically indicated.

Samples to be collected on C12D28 $\pm$ 2 days, if overlapping with C13D1 visit, samples should be taken prior to study treatment administration on C13D1.

TSH test to be performed locally at screening, C4D1 and end of treatment. Additional TSH test maybe performed as clinically indicated based on the symptoms as judged by the investigator.

CD19 positive lymphoma (as per local institutional guidelines) on a biopsy taken after completing prior CD19 targeted therapy. The local pathology report indicating DLBCL diagnosis and CD19 positivity will determine a patient's eligibility for study enrollment. In this patient group, a sample of this most recent biopsy should be provided for central pathology confirmation of both DLBCL diagnosis and CD19 expression. Only the most recent biopsy needs to be provided, it is not necessary to provide tissue taken at different stages of disease.

